6.4.3. Early Termination Visit

Subjects prematurely discontinuing from the study should complete an early termination (ET) visit within 30 days of last dose.

If a subject discontinues study dosing (for example, as a result of an AE), every attempt should be made to keep the subject in the study and continue to perform the required study-related procedures per the Study Procedures Table (see [Appendix 2](#)). If a subject who discontinues study dosing and continues to perform the required study-related procedures decides to prematurely discontinue from the study, an ET visit should be completed within 30 days of last study visit.

Subjects should be instructed to fast (no food or drink, except water), starting from midnight (00:00) or earlier, as appropriate, on the evening prior to the ET visit to ensure an approximate 8-hour fast prior to the fasted blood sample collection the next morning.

The following treatment procedures/assessments are to be completed and documented at this visit.

[REDACTED]

[REDACTED]

[REDACTED]

- For subjects with history of IBD (as appropriate, see Section [6.8.6](#)):

IBD symptom severity assessment

any evidence of active IBD seen on routinely performed colonoscopy will be captured

- Symptom-driven physical examination including ascites and HE assessments
- Record vital signs body weight
- Obtain blood samples for:

Chemistry

eGFR

Hematology

Coagulation Panel

Lipid Profile

C-peptide, Insulin and HbA_{1c}

Biomarkers

CCI [REDACTED]

- Obtain urine samples for:

Urine pregnancy test for females of child bearing potential only

- Perform FibroScan
- CP and MELD scores
- Review study drug compliance

Reconcile study drug administration using pill counts

All study drugs should be returned at this visit

- Record all CMs that the subject has taken since the previous visit
- Record any SAEs and all AEs occurring since the previous visit

6.4.4. Follow- Up Visit (\pm 5 Days)

Subjects will return for a follow-up visit 4 weeks after the Week 12 or ET visit.

Subjects should be instructed to fast (no food or drink, except water), starting from midnight (00:00) or earlier, as appropriate, on the evening prior to their visits to ensure an approximate 8-hour fast prior to the fasted blood sample collection the next morning.

The following will be performed and documented at this visit.

- Pruritus assessments (Pruritus VAS and 5D-Itch)
- For subjects with history of IBD (as appropriate, see Section 6.8.6):

IBD symptom severity assessment

any evidence of active IBD seen on routinely performed colonoscopy will be captured

- Symptom-driven physical examination including ascites and HE assessments
- Record vital signs, body weight
- Obtain blood samples for:

Chemistry

eGFR

Hematology

Coagulation Panel

Lipid Profile

C-peptide, Insulin and HbA_{1c}

Biomarkers

- CP and MELD scores
- Obtain urine samples for:

Urine pregnancy testing for females of childbearing potential only

- Record all CMs that the subject has taken since the previous visit
- Record any SAEs and all AEs occurring since the previous visit

6.4.5. Unscheduled Visit

Additional unscheduled assessments may be performed at the discretion of the investigator.

Subjects returning to the clinic for an unscheduled visit will be instructed to fast (no food or drink, except water), starting from midnight (00:00) or earlier, as appropriate, on the evening prior to the visit to ensure an approximate 8-hour fast prior to the fasted blood sample collection the next morning.

Subjects should also be instructed to HOLD their dose of study drug on the day of an unscheduled visit until all blood samples have been completed. Unscheduled visits may also occur while on a PI approved study drug dose interruption as detailed in Section [6.4.2](#).

At a minimum, the following will be performed and documented.

- For subjects with history of IBD (as appropriate, see Section [6.8.6](#)):

IBD symptom severity assessment

any evidence of active IBD seen on routinely performed colonoscopy will be captured

- Symptom-driven physical examination including ascites and HE assessments
- Record vital signs and body weight
- Obtain blood samples for:

Chemistry

Hematology

eGFR

- Record all CMs that the subject has taken since the previous visit
- Record any SAEs and all AEs occurring since the previous visit

If the Unscheduled visit is performed for the sole purpose of distribution of study drug, the assessments noted above do not need to be performed.

6.5. Assessments for Premature Discontinuation from Study

If a subject discontinues study dosing (for example, as a result of an AE thought to be related to study drug), every attempt should be made to keep the subject in the study and continue to perform the required study-related procedures per the Study Procedures Table (see [Appendix 2](#)). If a subject who discontinues study dosing and continues to perform the required study-related procedures decides to prematurely discontinue from the study, an ET visit should be completed within 30 days of last study visit. If this is not possible or acceptable to the subject or investigator, the subject may be withdrawn from the study.

6.6. Criteria for Discontinuation of Study Treatment

Study medication may be discontinued in the following instances:

- Intercurrent illness that would, in the judgment of the investigator, affect assessments of clinical status to a significant degree following resolution of intercurrent illness, the subject may resume study dosing at the discretion of the investigator.
- Unacceptable toxicity (Section 7.5), or toxicity that, in the judgment of the investigator, compromises the ability to continue study-specific procedures or is considered to not be in the subject's best interest
- Any subject without a history of IBD who develops new onset IBD while participating in the study, or any subject with a history of IBD who experiences a clinically significant worsening in IBD symptoms (eg, stool frequency, bleeding) or endoscopic evidence of disease worsening in the opinion of the PI.
- CP score ≥ 7 on two consecutive occasions at least two weeks apart unless due to an alternate etiology (eg, therapeutic anticoagulation), refer to Section 7.5
- Any subject who experiences a hepatic decompensation event, including ascites, HE, or portal hypertension-related upper gastrointestinal bleeding (eg, bleeding from esophageal varices, gastric varices, or portal hypertensive gastropathy)
- Subject request to discontinue for any reason
- Subject noncompliance
- Significant protocol deviation that impacts subject safety
- Pregnancy during the study; refer to Appendix 4
- Discontinuation of the study at the request of Gilead, a regulatory agency or an IRB or IEC

CC1

CCI

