7.5.2. Close Observation

[figure not shown]
Close observation includes:

- Repeating liver biochemistries (CCI [REDACTED]) and obtaining a CPK level within 48-72 hours of confirmatory results collected prior to entering close observation.
- Obtaining a more detailed history of symptoms and prior or concurrent disease
- Obtaining a history of CM use (including nonprescription medications and herbal and dietary supplement preparations), alcohol use, recreational drug use, and special diets
- Obtaining a history of exposure to environmental chemical agents
- Ruling out other causes of liver disease as needed (obtain viral hepatitis panel, imaging for evaluation of biliary tract disease, etc. if required in the opinion of the investigator)
- Continue to monitor liver biochemistries at least twice weekly. Frequency can decrease to once a week or less if abnormalities stabilize or study drugs have been discontinued and the subject is asymptomatic.

During a period of close observation for DILI, study drugs can be continued, if desired, at the discretion of both the medical monitor and investigator.

If on-treatment elevations of ALT and/or AST exceed the values shown in [Figure 7-2](#), are confirmed on repeat testing within 48-72 hours of results, and no alternative cause is immediately apparent, the subject must be placed into close observation and study drug must be withheld.

Figure 7-2. On-Treatment Monitoring Requiring Withholding of Study Drugs

* Unless subject has Gilbert's syndrome, in which case a direct bilirubin > 2 x baseline (average of Screening & Day 1 values) will be used instead of total bilirubin.
**If not on therapeutic anticoagulation (e.g. warfarin). If on therapeutic anticoagulation, INR criteria is disregarded.

Abbreviations:

ULN – Upper limit of normal range
TB – Total Bilirubin

If study drugs are withheld, they may be reintroduced with approval from the Gilead medical monitor. In instances where study drug is withheld in the context of DILI, up to a 4-week study drug dose interruption is permitted. Upon resuming study drug, the subject should restart at prior dose as outlined in [Section 3](#).

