7.5.3. Child-Pugh Score

If a subject has an increase in their CP score to ≥ 7 , this should be confirmed with repeat testing within 48-72 hours of receipt of results. If confirmed, the medical monitor should be notified, and the subject should be placed into close observation as described above, unless an alternate etiology (eg, therapeutic anticoagulation) is identified. If the CP remains ≥ 7 for at least 2 consecutive weeks, and an alternate etiology has not been identified, study drug must be discontinued.

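### Section 6.6 makes stopping for Child-Pugh ≥7 and for pregnancy permissive where Section 7.5.3 and Appendix 4 make it mandatory, and times the Child-Pugh rule differently; Section 1.5 names a pruritus dose reduction that the readable operative text lacks

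*Protocol*

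**What the plan says.** **Obligation.** Protocol Section 6.6 opens with "Study medication may be discontinued in the following instances". Its list includes CP of 7 or more "on two consecutive occasions at least two weeks apart unless due to an alternate etiology (eg, therapeutic anticoagulation), refer to Section 7.5" and "Pregnancy during the study; refer to Appendix 4". Section 7.5.3 says that if CP stays at 7 or more "for at least 2 consecutive weeks, and an alternate etiology has not been identified, study drug must be discontinued". Appendix 4, item 5, says that a subject who is pregnant, or suspects it, must tell the investigator and stop study drug at once.

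**Child-Pugh timing.** Section 6.6 asks for two consecutive occasions at least two weeks apart and mentions no confirmatory test. Section 7.5.3 has steps: after a rise to 7 or more, "this should be confirmed with repeat testing within 48-72 hours of receipt of results". If the rise is confirmed, the medical monitor is told and "the subject should be placed into close observation as described above", unless another cause is found. The stopping rule then applies if CP stays raised for the 2 weeks.

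**Pruritus.** Section 1.5 presents pruritus as the primary risk of treatment and describes a formal plan made up of temporary interruption, dose reduction and supportive drugs. Section 7.5.4 gives supportive measures only. Section 7.5.5 and Appendix 2 note b allow one interruption of up to 4 weeks, then a 4-week re-challenge at the dose the subject was on. Section 7.5.5 adds stopping if a further related event would need another interruption. None of the three contains a step down in dose.

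**The concern.** These are rules for stopping or changing treatment in patients with cirrhosis. A site that works from Section 6.6, the section headed as the criteria for discontinuation, finds a discretionary verb and a CP criterion that can be satisfied on a different day from the one in Section 7.5.3. Two sites with identical results could then act a few days apart, each following the protocol.

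The pruritus point is of another kind. The risk/benefit section relies on a plan to mitigate the main risk, and one element of that plan has no rule in the readable sections that a site would use to carry it out.

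**Working it through.** No figure in the plan needs reproducing, since the protocol has no power calculation and this point rests on none. The check compares the texts and counts days.

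**1. Obligation**

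| Trigger | Section 6.6 | Other section |
|---|---|---|
| CP of 7 or more, persistent, no other cause | may stop; refers to 7.5 | 7.5.3: must stop |
| Pregnancy | may stop; refers to Appendix 4 | Appendix 4: must stop at once |

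The exception for another cause is essentially the same in 6.6 and 7.5.3, so the difference is in the verb and the timing.

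**2. Child-Pugh timing**

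Inputs:
- First CP of 7 or more on Day 0.
- Confirmatory repeat on Day d, with d = 2 or 3 (48-72 hours, Section 7.5.3). This assumes that results are received on the day of sampling.
- CP still 7 or more at every later score, with no other cause found.
- Both sections use two weeks, that is, 14 days.

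Rules:
- Section 7.5.3 is met at 0 + 14 = Day 14 if the 2 weeks run from the first result. It is met at d + 14 = Day 16 or 17 if they run from the repeat.
- The 6.6 bullet is met when two consecutive counted occasions are at least 14 days apart. If the repeat is not counted, Day 0 and Day 14 suffice. If it is counted, the gaps at a Day 14 score are d and 14 − d, that is, 2 and 12 days or 3 and 11 days, all below 14. The earliest day on which a score can pair with the repeat is d + 14 = Day 16 or 17.

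| Repeat counts as an occasion in 6.6? | 2 weeks in 7.5.3 run from | 7.5.3 met | 6.6 bullet met, earliest | Difference |
|---|---|---|---|---|
| Yes | first result | Day 14 | Day 16-17 | 6.6 later by 2-3 days |
| Yes | repeat | Day 16-17 | Day 16-17 | none |
| No | first result | Day 14 | Day 14 | none |
| No | repeat | Day 16-17 | Day 14 | 6.6 earlier by 2-3 days |

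The sections agree when the repeat is treated the same way in both. The first row matters most: 7.5.3 already requires stopping while the 6.6 bullet is unmet. In the last row 6.6 merely permits an earlier stop, so no required stop is missed.

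Two limits apply. Day 16-17 is the earliest day, with no counted score between the repeat and that day; a counted Day 14 score would push it later by an amount that depends on when CP is next scored. If results arrive L days after sampling, the repeat falls on Day L + 2 to L + 3 and the first-row gap, counted from sampling, becomes L + 2 to L + 3 days. The documents do not give L.

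**3. Pruritus**

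| Action | Section 1.5 | Sections 7.5.4, 7.5.5, Appendix 2 note b |
|---|---|---|
| Supportive care | yes | yes |
| Temporary interruption | yes | yes, once |
| Dose reduction | yes | not found |
| Re-challenge at the same dose | not mentioned | yes |
| Stop on a second related event needing interruption | not mentioned | yes (7.5.5) |

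The only other explicit dose-reduction text, in Section 1.2.7, describes the extension phase of a different study (GS-US-428-4025).

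**The case against.** The strongest reply is that *may* and *must* can both be obeyed. Every stop required by 7.5.3 or Appendix 4 is allowed by 6.6. The same lead-in covers a subject's own request and a request from a regulator or IRB, where site discretion makes little sense, so the list is best read as grounds for stopping. Both bullets point to the mandatory text, and "Unacceptable toxicity (Section 7.5), or toxicity that, in the judgment of the investigator" also brings a 7.5.3 stop within 6.6. Most of this stands: the verb is a mismatch that a careful reader can resolve, not a rule that prevents a required stop. What remains is that a cross-reference does not say which wording governs.

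On timing, the reply is that the gap is small, and that the medical monitor is notified once a raised CP is confirmed, which is a central check. Both are right. The difference is 0 to 3 days on the stated assumptions.

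On pruritus, Section 1.5 is narrative, not an instruction to sites, and Section 6.7 is redacted. That limits the claim to the readable text. Sections 7.5.4 and 7.5.5, where such a rule would be expected, are readable.

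Four stronger readings are tempting, and the documents do not support them:

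- *The 6.6 bullet might never be met.* A reader might infer this from "Continue to monitor liver biochemistries at least twice weekly", since consecutive tests would always be days apart. It needs a CP score at every close-observation test. CP requires INR and grading of ascites and encephalopathy (Section 6.8.5). The readable part of 7.5.2 asks for liver biochemistries and CPK, and the unscheduled-visit minimum in 6.4.5 has neither a coagulation panel nor a CP score. Monitoring may also fall to weekly or less often.
- *The bullet might be met by two raised scores with a normal repeat between them.* That means ignoring the normal repeat when judging consecutive occasions, which is not the natural reading.
- *The safety tables might change.* SAP 7.1.6 counts subjects with adverse events leading to discontinuation, not time to stopping, so a stop 2-3 days later is counted once either way. Under Protocol 7.6.2.1, pregnancy is not itself an adverse event.
- *Appendix 2 note b and 7.5.5 might name different re-challenge doses.* Note b restarts the challenge on the dose it has just named and refers to 7.5.5, so the two can be read together.

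**Conclusion.** The point holds as a set of internal inconsistencies that should be reconciled. Section 6.6 is permissive where 7.5.3 and Appendix 4 are mandatory, softened but not removed by the cross-references. The CP criterion is worded in two ways that can separate by 2-3 days, depending on whether the repeat counts as an occasion and on which result starts the 2 weeks; treated alike, the two rules agree. That size rests on same-day results, CP staying at 7 or more throughout, and scores falling on the days shown. Section 1.5 names a dose reduction for which the readable operative sections give no rule; Section 6.7 cannot be checked.

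No number of affected subjects can be given: about 20 were planned, enrollment was terminated early on 30 July 2021, and the documents do not state how many enrolled.

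**What to change.** Reconcile Section 6.6 with 7.5.3 and Appendix 4 so that the obligation to stop and the CP timing are stated once and identically. Say whether the 48-72 hour repeat counts as an occasion and from which result the 2 weeks run. Reconcile Section 1.5 with 7.5.4, 7.5.5 and Appendix 2 note b on whether dose reduction is permitted. The sponsor decides which clinical rule applies.

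The cost is a wording clarification, with no added procedures or patients. If dose reduction is kept, SAP 3.7.1 should be reread, because it numbers post-interruption days by the dose level at which the interruption occurred. With enrollment closed, if the protocol can no longer be amended, the clinical study report can state which reading was applied.

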6.8. Procedures and Specifications

6.8.1. Clinical Laboratory Analytes

Chemistry:

Alanine aminotransferase, AST, albumin, ALP, bicarbonate, blood urea nitrogen (BUN), calcium, chloride, creatinine, glucose, lactate dehydrogenase (LDH), magnesium, phosphorus, potassium, sodium, total and direct bilirubin, total protein, uric acid, GGT

eGFR:

eGFR is estimated by creatinine clearance calculated by the Cockcroft-Gault equation
{Cockcroft 1976}.

$$\text{Male: eGFR (mL/min)} = \frac{[140 - \text{age (years)}] \times \text{BW(kg)}}{72 \times \text{S}_{\text{cr}}}$$

$$\text{Female: eGFR(mL/min)} = \frac{[140 - \text{age (years)}] \times \text{BW(kg)} \times 0.85}{72 \times \text{S}_{\text{cr}}}$$

BW body weight; S_{cr} serum creatinine (mg/dL)

Actual body weight will be used for the eGFR.

Hematology:

Hematocrit, hemoglobin (Hb), platelet count, red blood cell count (RBC), white blood cell count (WBC) with differential (absolute and percentage) including lymphocytes, monocytes, neutrophils, eosinophils, basophils, and reticulocyte count and mean corpuscular volume.

Coagulation Panel:

Prothrombin time, partial thromboplastin time (PTT), and INR.

Pregnancy Tests:

Serum beta human chorionic gonadotropin (β -hCG) or urine β -hCG (if positive, requires immediate confirmation with serum β -hCG), and serum FSH.

Additional Tests:

C-peptide, insulin and HbA_{1c}, Lipid Profile, HIV-1 (reflex to HIV-1 RNA), HBV (HBsAg) and HCV (reflex to HCV RNA) serology, eGFR as calculated by modification of diet in renal disease (MDRD), urine drug screen (for amphetamines, cocaine, opiates), stool collection (if available), genomic sample collection, and creatine phosphokinase (CPK) testing (for Close Observation as needed per Section 7.5.2).

Biomarker tests:

- Inflammation high sensitivity C-reactive protein (hsCRP)

[REDACTED]

[REDACTED]

[REDACTED]

[REDACTED]

CCI

[REDACTED]

[REDACTED]

[REDACTED]

[REDACTED]

[REDACTED]

6.8.2. Medical History

Medical history including details regarding illnesses and allergies, date(s) of onset, and whether condition(s) is currently ongoing, and medication history, including nicotine and alcohol use, will be collected on all subjects during screening.

6.8.3. Physical Examination

A complete physical examination should include source documentation of general appearance, and the following body systems: head, neck, and thyroid; eyes, ears, nose, throat, mouth, and tongue; chest (excluding breasts); respiratory; cardiovascular; lymph nodes; abdomen; skin, hair, nails; musculoskeletal and neurological, and assessments for ascites & HE.

The focus of a symptom-driven physical examination should include assessments for ascites and HE and will be determined by the investigator based on subject complaint. For example, if a subject complains of a cough a respiratory exam should be performed. If consistent with pneumonia (eg, rales or crackles are identified) then an AE would be documented.

Height and body weight will be collected at specified time points.

6.8.4. Vital Signs

Assessment of vital signs will include measurement of resting blood pressure, pulse, respiratory rate and temperature.

Blood pressure will be measured using the following standardized process:

- Subject should sit for \geq 5 minutes with feet flat on the floor and measurement arm supported so that the midpoint of the manometer cuff is at heart level;
- Use a mercury sphygmomanometer or automatic blood pressure device with an appropriately sized cuff with the bladder centered over the brachial artery;
- Measure and record the blood pressure to the nearest 2 millimeter of mercury (mmHg) mark on the manometer or to the nearest whole number on an automatic device.

6.8.5. Clinical Liver Assessments

The MELD and CP scores will be calculated from the central laboratory values attained at each visit. CP will be calculated by the site at screening to assess eligibility; MELD may also be calculated by the sites at screening to determine eligibility if the central laboratory is unable to perform the calculation. MELD will be monitored by site at each visit for safety. Assessment of ascites and HE will be determined by the site at all visits as in the [Table 6-1](#) and will be entered into the eCRF. Dialysis in the preceding week will also be determined by the site at each visit. HE will also be assessed using the West Haven Criteria ([Appendix 5](#)).

Table 6-1. Child-Pugh (CP) Classification of the severity of cirrhosis

| | 1 | 2 | 3 |
|-----------------------------|--|--|---|
| Hepatic Encephalopathy (HE) | None No encephalopathy and not on any treatment for hepatic encephalopathy | Medication-Controlled Subject is lethargic, may have moderate confusion Subject is receiving medical therapy for HE | Medication-Refactory Marked confusion/incoherent, rousable but sleeping or comatose |
| Ascites | None No ascites and not on treatment for ascites | Mild/Moderate Cross sectional imaging showing ascites Abdominal distension Medication for ascites | Severe (diuretic-refractory) Visible clinically |
| Bilirubin (mg/dL) | < 2 | 2-3 | > 3 |
| Albumin (g/dL) | > 3.5 | 2.8-3.5 | < 2.8 |
| INR | < 1.7 | 1.7-2.3 | > 2.3 |

CP score is obtained by adding the score for each parameter.

CP class: A 5-6 points
 B 7-9 points
 C 10-15 points

The MELD score will be calculated by using the following formula:

$$10 \times ((0.378 \times \ln (\text{Total Bilirubin (mg/dL)})) + (1.12 \times \ln (\text{INR})) + (0.957 \times \ln (\text{Serum Creatinine (mg/dL)})) + 0.643).$$

Serum creatinine in $\mu\text{mol/L}$ will be converted to mg/dL by multiplying by 0.01131. Total bilirubin in $\mu\text{mol/L}$ will be converted to mg/dL by multiplying by 0.05848. Round total bilirubin to 1 decimal place and serum creatinine to 2 decimal places prior to using values in formula or calculation criteria.

[figure not shown]
If the serum creatinine is < 1.00 mg/dL, the calculation will use 1.00 as the serum creatinine value. If the serum creatinine is > 4.00 mg/dL or if “For subjects on dialysis, did the subjects have 2 or more dialysis treatments within the prior week?” is answered as “Yes”, the calculation will use 4.00 as the serum creatinine value. If the total bilirubin is < 1.0 mg/dL, the calculation will use 1.0 as the total bilirubin value. If the INR is < 1.0 , the calculation will use 1.0 as the INR value. If the creatinine is resulted as “Icteric Test Not Performed”, the calculation will use serum enzymatic creatinine.

The online calculator <https://www.mdcalc.com/meld-score-original-pre-2016-model-end-stage-liver-disease> may also be used.

